#### 7.3 SAMPLE SIZE/POWER AND TRIAL DURATION.

Twelve evaluable patients will be enrolled on the feasibility portion of the trial. We estimate having to screen/enroll 18 subjects to reach the goal of 12 evaluable subjects. If feasibility and safety are acceptable, then an additional 38 patients will be enrolled for a study total of 50 patients. We may have to screen/enroll up to 50 subjects to have an additional 38 patients participate in the phase II portion of the trial. We estimate that the first 12 patients will be enrolled in 1 year. Then the study will be suspended for patient observation for 2 months for feasibility and safety evaluation. If the feasibility study is acceptable, then accrual will continue. With an accrual of 12 patients per year, the study should be actively enrolling for 4 years. To test whether the 12 month rate of severe fatigue is lower than 50%, a one sample test will be performed. With 50 patients, there is 79% power to detect a 33% rate versus a null rate of 50% by chi-square test at 1-sided 5% significance.

For the feasibility study, the initial target sample size of 12 patients will be revised to 12 additional base of skull patients to be treated with pencil beam protons and evaluated for feasibility by the new definition. There will not be a target sample size for spine patients and we will enroll those patients while filling the enrollment goal for the base of skull patients. It is anticipated that up to 5 spine patients may be enrolled. The total enrollment to the feasibility study after this amendment will be up to 17 patients (12 base of skull and 5 spine).

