### **3.4** Early Withdrawal of Subjects

### 3.4.1 When and How to Withdraw Subjects

- Recurrent or Progressive Disease: Subjects who have clinical or radiologic evidence of recurrent disease will undergo an evaluation to document the nature of the abnormality. If recurrent or progressive cancer is diagnosed, the subject will be considered off study at that time.
- PI Decision: Subjects may be withdrawn at any time during the study if the PI believes it is in the subject's best interest. In this event, the reasons for withdrawal will be documented.
- Subject Participation: Refusal to continue treatment, follow-up, comply with the protocol or withdrawal of consent. In this event, the reasons for withdrawal will be documented.
- Adverse Event (including intercurrent illness, unacceptable toxicity).

Once the subject has discontinued treatment, the primary reason for discontinuing treatment must be clearly documented in the subject's records and on the CRF. The investigator will assess each subject for response at the time of withdrawal.

Every effort will be made to follow all subjects off study for toxicity and survival unless patient withdraws consent. If subjects withdraw from the study at any time, we will ask for his/her written permission to continue to access medical records for overall survival. Acute toxicities will be assessed for 90 days from the first date of treatment. Survival will be followed for a minimum of 5 years.

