#### 7.2.4 Statistical Analyses.

Analyses of acute and late toxicity and fatigue will be completed within 1 year of completion of accrual. Time-to-event outcomes and long term longitudinal measurements of fatigue and neurocognitive function will be analyzed 2-3 years after completion of accrual. Descriptive analyses and subset analyses are likely. The purpose of these subset analyses is hypothesis generation. Subgroup analyses will likely describe time-to-event outcomes by histology (e.g., chordoma or chondrosarcoma) and extent of surgery (e.g., biopsy only, partial debulking, and maximal debulking). They will produce estimates of clinical outcomes, to aid in the design of future clinical trials.

Acute and Late Toxicity. All acute and late toxicities will be graded by CTCAE Version 4.0 and tabulated. Toxicity rates and 95% confidence intervals will be calculated. The maximum half-width of the 95% confidence interval is  $\pm 14\%$  based on 50 patients.

Time-to-Event Outcomes. Trials of chordomas and chondrosarcomas which combine proton with photon, have demonstrated 5-year progression-free survival rates (i.e., free of local failure) of 60-80%. We do not expect the 5-year PFS rate to be much different with protons. Progression-free and overall survival and time to local failure, will be estimated by the Kaplan-Meier method. Median and 5-year estimates and 95% confidence intervals will be calculated.

Fatigue (Brief Fatigue Inventory, BFI) & Neurocognitive function (FACT-Br) will be summarized by mean and standard deviation calculated and plotted over time. We will examine the plots for the expected worsening of function in the 6-12 months post-radiation and gradual improvement from 12-24 months. Pre- and post-treatment comparisons at a primary time point (e.g., at 24 months post-radiation when function should have recovered) will be evaluated by Student's paired t-test or nonparametric Wilcoxon signed ranks test. A general strategy to assess trends over time in longitudinal data is to employ linear mixed effects models, which can account for the impact of covariates such as anti-seizure medication and baseline performance status. The BFI can also be categorized as mild (1-3), moderate (4-6) and severe (7-10). The rates of patients in the severe category will be estimated at each time point. Of primary interest are the rates at 12 and 24 months post-treatment.

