There are little data published on BFI and FACT-Br scores in chordoma patients treated with radiotherapy, but profound fatigue and neurocognitive impairment are known side effects of photon radiation. We anticipate that the rate of severe fatigue will be reduced with protons. We will perform one exploratory test to determine whether the 12 month rate of severe fatigue is lower than 50%.

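### Section 7.3's fatigue test cannot have both 79% power and a 5% level at n = 50, and the figure assumes every patient has a 12-month BFI

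*Combined protocol and SAP*

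**What the plan says.** Section 7.3 sets out the test and its power: "To test whether the 12 month rate of severe fatigue is lower than 50%, a one sample test will be performed". It continues that with 50 patients "there is 79% power to detect a 33% rate versus a null rate of 50% by chi-square test" "at 1-sided 5% significance". No rejection cut-off is given, and the plan does not say whether the test is exact, continuity-corrected or uncorrected. Section 7.2.4 labels this a single exploratory test and lists the 12-month severe-fatigue rate among the quantities of main interest. It is the plan's only power statement.

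Four other statements bear on how many patients will have a 12-month BFI:

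- **Off-study rule.** Under Section 3.4.1, when recurrence or progression is diagnosed, "the subject will be considered off study at that time". Off-study patients are then to be followed for toxicity and survival. The BFI is not mentioned.
- **Evaluability.** In the feasibility part, Section 7.1.1 counts a subject as evaluable on reaching the first follow-up visit. The enrolment allowances in Section 7.3 (18 for 12, and up to 50 for 38) cover evaluable or participating patients, not patients with a 12-month BFI.
- **Timing.** Section 7.2.4 says "Analyses of acute and late toxicity and fatigue will be completed within 1 year of completion of accrual". Long-term longitudinal fatigue data are to be analysed 2–3 years after accrual. The section does not say to which of the two analyses the 12-month test belongs.
- **Total.** Section 7.3 says that after the 12 feasibility patients, "then an additional 38 patients will be enrolled for a study total of 50 patients". Section 7.1.4, as amended, refers to 26 treated feasibility patients.

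**The concern.** With 50 binary outcomes the number of severe cases is a whole number, so the attainable significance levels come in steps. A power figure from a smooth approximation may then describe no rule that can actually be applied. Here the result would turn on an unstated choice: 19 severe cases out of 50 would be significant by the uncorrected chi-square test and not significant by an exact test at 5%.

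Separately, a power figure based on the enrolled number is optimistic if the plan's own follow-up rules and analysis date mean that some patients have no month-12 measurement. What is at stake is whether the plan's one power statement describes the test that will be run on the patients who will be assessed.

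**Working it through.** **Inputs.** From Section 7.3: null rate 0.50, alternative 0.33, n = 50, one-sided 5%, chi-square test. From Section 7.2.4: five-year PFS 60–80% and the timing of the fatigue analysis. From Section 4.6: treatment usually completed within 9 weeks. From Sections 3.3 and 7.3: accrual of 12–15 patients a year.

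**1. The plan's figure.** The normal approximation for the one-sample chi-square (score) test without continuity correction is

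Power = Φ{[(p0 − p1)√n − 1.645√(p0q0)] / √(p1q1)}

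= Φ{[0.17 × 7.071 − 1.645 × 0.5] / √(0.33 × 0.67)}

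= Φ{(1.2021 − 0.8224) / 0.4702} = Φ(0.807) = 79.03%.

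The stated 79% reproduces.

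**2. What each cut-off delivers at n = 50.** Let X be the number with severe fatigue. Size is P(X ≤ c) at 0.50, and power is P(X ≤ c) at 0.33.

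| Reject if X ≤ | z, uncorrected | True size | True power |
|---|---|---|---|
| 18 | −1.98 | 3.25% | 73.0% |
| 19 | −1.70 | 5.95% | 81.7% |
| 20 | −1.41 | 10.13% | 88.4% |

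The uncorrected chi-square test needs z ≤ −1.645, so it rejects at 19 or fewer. The largest cut-off with true size at or below 5% is 18. The stated 79% falls between these two rules and belongs to neither.

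**3. How many patients might have a 12-month BFI.** The visit falls about 14 months after the start of radiation (9 weeks of treatment plus 12 months). The documents give no progression figure at that time, so I assume a constant hazard from the five-year PFS:

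- PFS 60%: 0.60^(14/60) = 0.888, and 50 × 0.888 = 44.4
- PFS 80%: 0.80^(14/60) = 0.949, and 50 × 0.949 = 47.5

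That is about 44–47 of 50, before missed visits or withdrawals.

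| n assessed | Plan's formula | Exact cut-off | Exact size | Exact power |
|---|---|---|---|---|
| 44 | 74.2% | 16 | 4.81% | 74.1% |
| 45 | 75.1% | 16 | 3.62% | 70.4% |
| 46 | 75.9% | 16 | 2.70% | 66.6% |
| 47 | 76.7% | 17 | 3.95% | 73.5% |
| 50 | 79.0% | 18 | 3.25% | 73.0% |

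Exact power is a sawtooth in n. At every n from 40 to 50 a test with true size at or below 5% has less than 79% power. The highest is 76.3%, at n = 49.

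**4. Timing.** The last patients reach the 12-month post-radiation visit about 14 months after starting treatment. An analysis completed within 12 months of the end of accrual therefore misses those entered in roughly the last two months. At 12–15 a year that is 2 × 12/12 = 2 to 2 × 15/12 = 2.5 patients, or about 2–3.

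**The case against.** The strongest defence is that 79% is the correct answer for the test the plan names. Run as an uncorrected chi-square test on 50 patients, that test has more power than stated (81.7%). The 73.0% appears only when an exact test is substituted, and much of the drop is discreteness, because the exact test uses 3.25% of its 5%. All of this stands. A reader might infer an arithmetic slip, or that the named test is underpowered at n = 50. Neither is supported: the fault of the named test at n = 50 is its size of 5.95%. Excess size and low power do not occur together there; each belongs to a different cut-off.

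The attrition count is also open to challenge, since the constant hazard is my assumption. Section 1.1 describes chordoma as slow-growing and cites a series with local relapse-free survival of 82% at 2 years and 50% at 5 years. A constant hazard from that 50% would predict 0.50^(24/60) = 76% at 2 years, so early loss in that series was smaller than such a model implies. That bears on the size of the loss, but not on the absence of any allowance for it. Nor does fewer patients always mean lower exact power: 74.1% at n = 44 exceeds 73.0% at n = 50.

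A reader might further infer that 50 assessed patients cannot be reached. The documents do not settle this. If 38 patients were added to the 26 feasibility patients, the total would be 64, and the plan's formula would give 87%. Other sections still say 50, so the denominator is unresolved rather than certainly too small.

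On timing, the later analysis at 2–3 years would include everyone's month-12 visit. The plan simply does not say which analysis carries this test.

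**Conclusion.** The point holds in a limited form. At n = 50, 79% power and a one-sided 5% level are not jointly attainable: the choice is 73.0% power at a true 3.25%, or 81.7% at a true 5.95%. This part is exact and rests only on the inputs in Section 7.3.

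The figure also presumes 50 month-12 BFI scores, which the off-study rule, the lack of any allowance for loss and the stated analysis date all work against. With 44–47 assessed, power is 74–77% by the plan's formula and about 67–74% exactly. That range depends on a constant hazard and on a total of 50.

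The consequence is modest. The test is exploratory, Section 7.2.1 describes phase II as characterising toxicity and summarising fatigue, and no continuation decision depends on the result.

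**What to change.** - In Sections 7.2.4 and 7.3, name an exact one-sided binomial test and give its cut-off: 18 or fewer severe cases if 50 are assessed, with the rule stated for other denominators.
- Restate power as about 73% at n = 50 (actual size 3.25%). Add the range for the number expected to have a 12-month BFI, about 67–74% for 44–47, with the attrition assumption stated.
- Say that this test is run once the last patient's 12-month BFI is in.
- Reconcile the total of 50 with the 26 feasibility patients in Section 7.1.4, and say which patients form the denominator.

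The cost is a change of wording, a less favourable power figure and about 2–3 months' delay for one exploratory test. No extra patients are needed.

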#### **Primary Objective**

The primary objective of this study is feasibility. The study will be deemed infeasible if greater than 10% of pts experience one of the following:

- a. Patient cannot be given treatment because anatomy is such that a dosimetrically satisfactory treatment plan cannot be devised as defined in Section 4.5.1.
- b. For base of skull patients only. Patient receives greater than 40% of their total treatment (for any reason, i.e. unable to set patient up within acceptable limits of tolerance, patient unable to tolerate treatment position or immobilization for duration of treatment) with photon beam radiotherapy (using a backup photon plan).

For spine and all other patients. Patient receives greater than 20% of their total treatment (for any reason, i.e. unable to set patient up within acceptable limits of tolerance, patient unable to tolerate treatment position or immobilization for duration of treatment) with photon beam radiotherapy (using a backup photon plan).

- c. Patient is unable to complete all of his/her treatments within 10 days of estimated date of treatment completion or requires a treatment break greater than 5 days.
- d. Additionally, no greater than 20% of patients experience an unexpected acute toxicity > Grade 3 that is probably or definitely related to radiation therapy.

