#### **Feasibility**

A feasibility rate  $\geq 90\%$  is considered acceptable. We will assume a beta (5,1) prior, which is information equivalent to feasibility established in 5 of 6 treated patients. If the number of patients in whom proton is deemed feasible is less than or equal to the number in the table below then termination will be considered as it is highly unlikely that the feasibility rate is  $\geq 90\%$ , as noted by the Bayesian posterior probabilities.

D ' D 1	C D '1 '1'	• ,				
Bayesian Rule	for Feasibili	ıty				
Patients treated in each stratum	3	6	9	1		
				2		
Patients in whom proton is	1	4	6	9		
feasible						
Posterior Prob[feasibility rate	0	0	0	0		
>90%]		•	•	•		
	0	0	0	0		
	4	9	4	8		
Action	Т	Terminate enrollment				

Acute toxicity will be divided into 2 categories to best characterize toxicities in this disease. Non-Neurologic Acute Toxicity

Because proton therapy is expected to spare normal tissues, a non-neurologic acute toxicity rate  $\leq 20\%$  is considered acceptable. We will assume a beta (1,5) prior, which is information equivalent to toxicity in of treated patients. If the number of patients with non-neurologic acute toxicity equals or exceeds the number in the table, then termination will be considered as it is likely that the toxicity rate is >10%, as noted by the Bayesian posterior probabilities.

Bayesian Rule for Non-Neurologic Acute Toxicity						
Patients treated	3	6	9	1		
				2		
Patients who experience acute	2	2	3	4		
toxicity						
Posterior Prob[toxicity rate	0	0	0	0		
>20%]			•			
	8	6	7	7		
	0	2	0	6		
Action	Te	Terminate enrollment				

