### 7.1.4 Statistical Analyses

Feasibility. The initial target sample size of 12 patients will be revised to 12 additional base of skull patients to be treated with pencil beam protons and evaluated for feasibility by the new definition. It is anticipated that up to 5 additional spine patients may be enrolled. So the total enrollment after this amendment will be up to 17 patients (12 base of skull and 5 spine). The statistical analysis will calculate the posterior probability that the feasibility rate is >90%. This analysis will be conducted 2 ways: based on all 26 patients treated and on all 17 patients treated after the modification. The definition of infeasibility will be that which was current when the patient enrolled on the trial. There will be no retroactive re-grading of infeasibility in the base of skull patients.

Acute Toxicity. All toxicities observed within 90 days from start of therapy will be graded by CTC Version 4.0 and tabulated. Special attention is paid to neurologic toxicity.

Late Toxicity. All toxicities observed later than 90 days from start of therapy will be graded by the CTCAE version 4.0 and tabulated.

Progression-free and overall survival will be estimated by the survival analysis methods. It is most likely that these time-to-event outcomes will be summarized as part of the phase II study.

Fatigue is scored on a 10-point scale based on the Brief Fatigue Inventory Questionnaire. At each time point, the BFI score will be summarized by mean and standard deviation, and plotted over time. We will examine the plots for the expected worsening of function in the 6-12 months post-radiation and gradual improvement from 12-24 months. The fatigue scores will be summarized in detail in the phase II study.

Neurocognitive function (FACT-Br) will be summarized by descriptive statistics and scatter plots. It is most likely that the neurologic outcomes will be summarized as part of the phase II study.

Estimation of Event Rates. The table below displays the 90% exact binomial confidence

intervals based on 12 patients treated.

intervals ous	ed on 12 patients	i catea.			
No. of	%	90%	No. of	%	90%
Events		exact	Events		exact
		CI			CI
0	0.0	17.5*	7	58.3	31.5,
					81.9
1	8.3	.43,	8	66.7	39.1,
		33.9			87.7
2	16.7	3.0,	9	75.0	47.2,
		43.8			92.8
3	25.0	7.2,	10	83.3	56.1,
		52.7			97.0
4	33.3	12.3,	11	91.7	66.1,
		60.9			99.6
5	41.7	18.1,	12	100.0	82.5*
		68.5			

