#### 7.2 PHASE II STUDY

Once feasibility and safety are established in the first 12 patients, then the phase II study will commence.

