### 7.2.3 Rules for Early Termination; continuation of rules as in 7.1.3

#### Non-Neurologic Acute Toxicity

If the number of patients with non-neurologic acute toxicity equals or exceeds the number in the table, then termination will be considered as it is likely that the toxicity rate is >20%, as noted by the Bayesian posterior probabilities.

Bayesian Rule for Non-Neurol	logic A	Acute Toxicit	У	
Patients treated	1	2	3	4

Version: 04/04/2014

Patients who experience acute toxicity Posterior Prob[toxicity rate >20%]	5 5 0	5 7 0	5 9 0	5 1 1 0
2070]	8	7	7	7
Action	0   T	6 Cerminate e	nrollment	1

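### The feasibility analysis pools base-of-skull and spine patients, so a pooled pass can hide a high spine failure rate

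*Combined protocol and SAP*

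**What the plan says.** Eligibility (Section 3.1) covers tumours of the skull and spine, and Section 7.2 does not narrow this for Phase II. Section 2(b) counts a base-of-skull patient as infeasible when more than 40% of treatment is given with photons. The other group has its own limit: "For spine and all other patients. Patient receives greater than 20% of their total treatment". Section 7.1.2.1 gives a single limit of 50% for everyone.

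The amended Section 7.3 sets a target of 12 further base-of-skull patients. On spine it says "There will not be a target sample size for spine patients and we will enroll those patients while filling the enrollment goal" for base of skull, and then "It is anticipated that up to 5 spine patients may be enrolled".

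The feasibility analysis in Section 7.1.4 is the posterior probability that the feasibility rate exceeds 90%: "This analysis will be conducted 2 ways: based on all 26 patients treated and on all 17 patients treated after the modification". Both sets mix the sites, and no pass level is given for either. Each patient is scored by the definition in force at enrolment.

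The stopping table in Section 7.1.3 has a row labelled "Patients treated in each stratum", with looks at 3, 6, 9 and 12. No stratum is defined anywhere. The gate in Section 7.2 has no condition by site: "Once feasibility and safety are established in the first 12 patients, then the phase II study will commence".

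**The concern.** When two groups are judged against different failure limits, a single pooled rate does not answer the question for the smaller one. Here spine supplies at most 5 of the 17 patients enrolled after the amendment and may supply none. Good base-of-skull results can carry the pooled figure past the criterion while a large share of spine patients fail their own limit. Feasibility is the primary objective and opens a Phase II that admits both sites. A reader told that protons were feasible would take this to cover spine, although the planned output would contain no spine result to check it against.

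**Working it through.** **1. The plan's own table.** With the Beta(5,1) prior, s feasible and f infeasible patients give P(rate > 0.90) under Beta(5+s, 1+f).

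| Look | Feasible at boundary | Posterior | Stated | One more feasible |
|---|---|---|---|---|
| 3 | 1 | 0.038 | 0.04 | 0.187 |
| 6 | 4 | 0.090 | 0.09 | 0.303 |
| 9 | 6 | 0.044 | 0.04 | 0.158 |
| 12 | 9 | 0.083 | 0.08 | 0.238 |

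The stated values reproduce. The table stops at about 0.09 or below. Any cut-off from 0.090 up to just under 0.158 would give the same table.

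**2. Literal 10% rule (Sections 2 and 7.1.2.1), post-amendment set.** 1/17 = 5.9% passes and 2/17 = 11.8% does not, so one failure is allowed. The same holds with 3 spine patients (10% of 15 is 1.5) and with 2 (10% of 14 is 1.4).

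Let the true spine infeasibility be 30% (an assumption). With 5 spine patients:
- P(0 spine failures) = 0.7^5 = 0.168
- P(at most 1) = 0.168 + 5(0.3)(0.7^4) = 0.528

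Let b be the base-of-skull failure rate. Then

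P(pass) = (1−b)^12 × P(at most 1 spine failure) + 12b(1−b)^11 × P(0 spine failures).

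- b = 0: 0.528
- b = 5%: 0.540 × 0.528 + 0.341 × 0.168 = 0.343
- b = 10%: 0.282 × 0.528 + 0.377 × 0.168 = 0.212

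| Spine patients | b = 0 | b = 5% | b = 10% |
|---|---|---|---|
| 5 | 53% | 34% | 21% |
| 3 | 78% | 54% | 35% |
| 2 | 91% | 66% | 44% |

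The interim looks do not change these figures, because no boundary in the table is crossed by a single failure.

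**3. Posterior rule.** Section 7.1.4 gives no cut-off at 17 or 26, so carrying over the table's level is an assumption.
- Pooled, n = 17: 0, 1, 2, 3 and 4 failures give 0.902, 0.661, 0.380, 0.172 and 0.062. Three failures pass, so 3 of 5 spine failures with 0 of 12 base-of-skull failures passes at 0.172.
- Spine alone, n = 5: 0, 1, 2 and 3 failures give 0.651, 0.264, 0.070 and 0.013. Two failures in 5 would already stop.

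These classifications hold for any cut-off in the range found in step 1. If the looks at 3, 6, 9 and 12 are applied to the pooled sequence, the three-failure case also needs at most 1 failure in the first 6 patients and at most 2 in the first 12.

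**4. Table read by site.** If spine is a stratum, 5 patients reach only the look at 3, which stops at 2 or more failures. At 30% infeasibility that look does not stop with probability 0.784. With fewer than 3 spine patients there is no look.

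**5. What 5 patients can show.** With 0 failures in 5, the one-sided 95% upper limit is 1 − 0.05^(1/5) = 0.451. With no spine patients, the posterior stays at the prior: 1 − 0.9^5 = 0.410.

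**The case against.** The strongest defence is that this is a disclosed, practical choice. Section 7.3 says openly that spine has no target. Section 3.3 reports about 12 cases a year of the two tumours together, and the rationale section describes the protocol's purpose as base-of-skull disease. A small, unpowered spine group is reasonable in that setting. This stands: the absence of a spine target is not the fault, and no extra spine patients are asked for.

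A reader might infer that spine patients enter Phase II with no evidence and that no rule could react. The documents do not support that. Section 7.1.3 allows the Bayesian probability to be calculated at any time. Its table label may imply a look by site. The acute toxicity boundaries continue into Phase II for all patients. The site mix of the 9 earlier patients (26 − 17) is not given, so some may have had spine tumours.

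A reader might also treat the lack of a Phase II feasibility table as a spine gap, since Section 7.2.3 is headed "continuation of rules as in 7.1.3" yet lists only toxicity. That absence applies equally to base of skull, and Section 2 makes feasibility the purpose of the first phase.

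Requiring 12 assessed spine patients, or running a spine stopping table through Phase II, would be a debatable trade. Four looks on 12 patients would stop about 16% of the time at exactly 10% infeasibility. If the 5/17 share continued at 12 patients a year, 12 spine patients would take 12 / (12 × 5/17) = 3.4 years of a four-year accrual.

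Finally, 53% is the case most favourable to the concern, because it assumes no base-of-skull failure. It should be quoted only with the 34% and 21%.

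**Conclusion.** The point holds as a gap in analysis and reporting. Both planned feasibility posteriors pool two sites that Section 2(b) scores differently, and the table's strata are undefined. A pooled pass is therefore weak evidence for spine.

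Under the literal 10% rule, with 5 spine patients at 30% true infeasibility, the chance of a pooled pass is 21% to 53% as the base-of-skull failure rate goes from 10% to 0. Under the posterior rule, 3 spine failures in 5 can pass when pooled, while 2 in 5 would fail on spine alone. The assumptions are the 30% rate, the base-of-skull rates and, for the posterior comparison, the table's stop level carried to 17 and to 5 patients.

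Describing the spine limit as the stricter one rests on Section 2(b) alone. Section 7.1.2.1 gives one limit for all sites, and this review takes no position on which is right.

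**What to change.** - **Before anything else:** reconcile the photon limits in Sections 2(b) and 7.1.2.1.
- **Section 7.1.3:** define the strata of the feasibility table as base of skull and spine.
- **Section 7.1.4:** alongside the pooled analyses, report for each site the number feasible out of the number treated, an exact confidence interval, and the posterior probability that feasibility exceeds 90%. Count earlier spine patients under the definition in force when they enrolled, as the section already requires.
- **Conclusion:** state that the formal feasibility conclusion applies to base of skull, and that spine feasibility is descriptive and shown with its wide interval.

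This is a change of wording and tabulation. Plan coverage, photon share and treatment breaks must already be recorded to score feasibility, so it needs no new data and no extra patients. The cost is that the feasibility claim becomes narrower.
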